- To evaluate the safety, tolerability, and dose-limiting toxicities (DLTs) of INCAGN01949 in combination with immune therapies and to define the recommended dose(s) of INCAGN01949 when given in combination with immune therapies.

Phase 2

- To evaluate the efficacy of INCAGN01949 when given in combination with immune therapies by assessing objective response rate (ORR) per RECIST v1.1.

Secondary Objectives:

Phase 1 and Phase 2

- To evaluate the efficacy of INCAGN01949 when given in combination with immune therapies by assessing ORR, duration of response, disease control rate (DCR), duration of disease control, and progression-free survival (PFS), per RECIST v1.1.
- To evaluate the safety and tolerability of INCAGN01949 when given in combination with immune therapies.

Primary Endpoints:

- Safety and tolerability will be assessed by monitoring frequency, duration, and severity of adverse events (AEs).
- ORR, defined as the percentage of subjects having complete response (CR) or partial response (PR), will be determined by investigator assessment of radiographic disease assessments per RECIST v1.1.

Secondary Endpoints:

- ORR, defined as the percentage of subjects having CR or PR, will be determined by investigator assessment of radiographic disease assessments per RECIST v1.1.
- Duration of response, defined as the time from the earliest date of disease response (CR or PR) until earliest date of disease progression or death due to any cause, if occurring sooner than progression, will be determined by investigator assessment of radiographic disease assessments per RECIST v1.1.
- DCR, defined as the percentage of subjects having CR, PR, or stable disease (SD), will be determined by investigator assessment of a radiographic disease assessments per RECIST v1.1.
- Duration of disease control (CR, PR, and SD) as measured from first report of SD or better until disease progression or death from any cause, if occurring sooner than progression, will be determined by investigator assessment of radiographic disease per RECIST v1.1.
- PFS, defined as the time from the start of combination therapy until the earliest date of disease progression or death due to any cause, if occurring sooner than progression, as determined by investigator assessment of objective radiographic disease assessments per RECIST v1.1.
- Safety and tolerability will be assessed by monitoring frequency, duration, and severity of AEs.

Overall Study Design:

[figure not shown]

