2.2.2. Secondary Endpoints

- ORR, defined as the percentage of subjects having CR or PR, will be determined by investigator assessment of radiographic disease assessments per RECIST v1.1.
- DOR, defined as the time from the earliest date of disease response (CR or PR) until earliest date of disease progression or death due to any cause, if occurring sooner than progression, will be determined by investigator assessment of radiographic disease assessments per RECIST v1.1.
- DCR, defined as the percentage of subjects having CR, PR, or SD, will be determined by investigator assessment of a radiographic disease assessments per RECIST v1.1.
- Duration of disease control (CR, PR, and SD) as measured from first report of SD or better until disease progression or death from any cause, if occurring sooner than progression, will be determined by investigator assessment of radiographic disease per RECIST v1.1.
- PFS, defined as the time from the start of combination therapy until the earliest date of disease progression or death due to any cause, if occurring sooner than progression, as determined by investigator assessment of objective radiographic disease assessments per RECIST v1.1.
- Safety and tolerability will be assessed by monitoring frequency, duration, and severity of AEs.

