7.7.1.1.2. Tumor Imaging During the Study

The first imaging assessment should be performed 8 weeks after the first dose of INCAGN01949 and then every 8 weeks (56 days \pm 7 days) for 12 months (until the Week 56 scan) and then every 12 weeks thereafter until disease progression is determined. Imaging assessments may be done more frequently if clinically indicated. **Imaging should not be delayed for delays in cycle starts.**

Per mRECIST, response may be confirmed by a repeat radiographic assessment not less than 4 weeks from the date the response was first documented. The scan for confirmation of response may be performed at the earliest 4 weeks after the first indication of response or at the next scheduled scan, whichever is clinically indicated.

Imaging should continue to be performed until documented disease progression, the start of new anticancer treatment, withdrawal of consent, death, or the end of the study, whichever occurs first. Disease progression may be confirmed at least 4 weeks, but no later than 6 weeks, after the first scan indicating progression in clinically stable subjects. Subjects who have unconfirmed disease progression may continue on treatment until progression is confirmed, provided that they have met the conditions detailed in Section 7.7.1. A central imaging vendor will not be used in this study.

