For determination of confirmed BOR, confirmatory scans with a response of NE will be subsequently followed by another scan at a minimum of 4 weeks. For example, in the case of PR at the first timepoint followed by NE at a subsequent timepoint, if a third scan shows a PR, then the confirmed BOR will be PR. There will be no third confirmatory scans performed for a loss of response. For example, if a response of PR at the first timepoint is followed by a response of SD or PD at a subsequent timepoint, the confirmed BOR will be determined using the rules in [Table 4](#).

Table 4: Derivation of Confirmed Best Overall Response

Overall Response at First Timepoint	Overall Response at Subsequent Timepoint	Confirmed Best Overall Response
CR	CR	CR
CR	PR	SD, PD, or PR ^a
CR	SD	SD, ^a provided minimum criteria for SD duration are met; otherwise, PD
CR	PD	SD, ^a provided minimum criteria for SD duration are met; otherwise, PD
CR	NE	SD, ^a provided minimum criteria for SD duration are met; otherwise NE
PR	CR	PR
PR	PR	PR
PR	SD	SD
PR	PD	SD provided minimum criteria for SD duration are met; otherwise, PD
PR	NE	SD, ^a provided minimum criteria for SD duration are met; otherwise NE
NE	NE	NE

^a If a CR is truly met at the first timepoint, then any disease seen at a subsequent timepoint, even disease meeting PR criteria relative to baseline, makes the disease PD at that point (since disease must have reappeared after CR). Confirmed BOR would depend on whether the minimum duration for SD was met. However, sometimes CR may be claimed when subsequent scans suggest small lesions were likely still present and in fact the subject had a PR, not a CR, at the first timepoint. Under these circumstances, the original CR should be changed to a PR, and the confirmed BOR is PR.

For subjects with measurable disease at baseline, the RECIST v1.1 assessment criteria presented in [Table 5](#) can be used to determine the overall disease status at a given timepoint based on the target lesion, nontarget lesion, and new lesion assessment.

Table 5: RECIST Evaluation Criteria for Overall Response: Measurable Disease at Baseline

Target Lesions	Nontarget Lesions	New Lesions	Overall Response
CR	CR	No	CR
CR	Non-CR/non-PD	No	PR
CR	NE	No	PR
PR	Non-PD or NE	No	PR
SD	Non-PD or NE	No	SD
Not all evaluated	Non-PD	No	NE
PD	Any	Yes or No	PD
Any	PD	Yes or No	PD
Any	Any	Yes	PD

7.3.2.1.1. Subgroup Analyses for Confirmed Best Overall Response Under RECIST v 1.1 in Phase 2

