Subgroups will be formed based on the following subject characteristics and baseline variables for Phase 2 response evaluable subjects whose data are available:

- PD-L1 expression within tumor type: high, negative/low, unknown
- Number of prior therapies for advanced and metastatic disease within tumor type
- Subjects with > 1 postbaseline scan within tumor type
- Tumor-type disease characteristics for RCC and urothelial carcinoma

7.3.2.2. Unconfirmed ORR and Unconfirmed BOR by RECIST v1.1 – Sensitivity and Supportive Analyses for Confirmed ORR and Confirmed BOR by RECIST v1.1

A sensitivity analysis for the ORR assessed under RECIST v1.1 will be performed using unconfirmed CRs and PRs. The unconfirmed BOR is defined as the best response recorded postbaseline before and including the first PD, in the order of CR, PR, SD, PD, and NE. For this definition, responses of CR and PR do not need to be confirmed at a subsequent timepoint. In the case of SD, measurements must meet the SD criteria at least once after the date of first dose at a minimum interval of 49 (56-7) days. Subjects that fail to meet this criterion will have BOR of PD if the next available assessment indicates PD or NE if there is no additional assessment available.

Unconfirmed ORR will be summarized by treatment group and tumor type as a sensitivity analysis for the primary endpoint ORR for the Phase 2 response evaluable population and as a sensitivity analysis for the secondary endpoint ORR for the Phase 1 response evaluable population.

7.3.2.2.1. Subgroup Analyses for Unconfirmed Best Overall Response by RECIST v 1.1 in Phase 1

For the sensitivity analysis for unconfirmed BOR, subgroups will be formed based on subjects' prior treatment with an anti-PD-1/PD-L1 therapy within their tumor type (Yes/No) for Phase 1 response evaluable subjects and whose data are available.

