7.3.4. Duration of Disease Control and Disease Control Rate

Duration of disease control (CR, PR, and SD) is defined as the time from the first report of SD or better until disease progression or death from any cause, if occurring sooner than progression, as determined by investigator assessment of radiographic disease per RECIST v1.1 and mRECIST. Note that the criteria for the assessment of PD in duration of disease control are the same with ORR, which are presented in Section [7.3.2.3](#).

The duration of disease control will be estimated with 95% CIs overall and by treatment group. Confidence intervals will be calculated based on the exact method for binomial distributions. Swim plots for duration of disease control will be generated separately for RECIST v1.1 and mRECIST criteria.

Disease control rate, defined as the proportion of subjects who have disease control (CR + PR + SD), as per RECIST v1.1 and mRECIST will be summarized. For the determination of DCR, response of CR and PR do not need to be confirmed at a subsequent timepoint. In the case of SD, measurements must meet the SD criteria at least after the date of first dose at a minimum of 49 days. Subjects who fail to meet this criterion will have confirmed BOR of PD if the next available assessment indicated PD or NE if there is no additional assessment available. Disease control rate will be estimated with 95% CIs.

Duration of disease control and DCR as assessed per RECIST v1.1 and mRECIST will be summarized by treatment group and dose level for the Phase 1 response evaluable population and by treatment group and tumor type for the Phase 2 response evaluable population.

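### SAP 7.3.4 lets stable disease first seen before Day 49 enter the duration of disease control, although the same section does not count it in the disease control rate

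*Protocol*

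**What the plan says.** The Protocol synopsis gives the endpoint as "Duration of disease control (CR, PR, and SD) as measured from first report of SD or better until disease progression" or death, and Protocol 2.2.2 has the same definition. SAP 7.3.4 repeats it as "defined as the time from the first report of SD or better until disease progression or death from any cause". Neither sets a minimum time for the SD that starts the clock.

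For DCR, SAP 7.3.4 adds a condition on SD: "measurements must meet the SD criteria at least after the date of first dose at a minimum of 49 days". A subject whose SD falls short becomes PD if the next assessment is PD, or NE if there is none. The source of the 49 days is shown in SAP 7.3.2.2: "minimum interval of 49 (56-7) days". SAP Table 4 carries the same idea into confirmed best response; for PR followed by PD, for example, the entry is "SD provided minimum criteria for SD duration are met; otherwise, PD".

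The Protocol's own DCR has no such minimum: "DCR, defined as the percentage of subjects having CR, PR, or stable disease (SD), will be determined by investigator assessment". The Protocol is therefore consistent with itself. The conflict lies within SAP 7.3.4, and between the SAP's DCR and the Protocol's.

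Protocol 7.7.1.1.2 places the first scan 8 weeks after first dose (window ±7 days), but "Imaging assessments may be done more frequently if clinically indicated". Protocol Table 12, footnote k, also asks for a scan at discontinuation for subjects who stop without confirmed progression, unless one was done in the preceding 4 weeks.

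SAP 7.3.4 summarises both measures in the Phase 1 response evaluable population. Appendix A Tables 2.1.1.1 and 2.1.1.2 put best response and duration of disease control in the same display.

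**The concern.** One section uses two membership rules for the same clinical state. The rate says that SD seen too early is not disease control. The duration accepts that SD as the start of disease control. A reader of Table 2.1.1.1 or 2.1.1.2 would expect the durations to belong to the subjects shown as having disease control, and nothing in the SAP ensures this.

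Duration of disease control is a Phase 1 secondary endpoint, and Protocol section 9 says the Phase 1 analyses will still be run. Results are given by treatment group and dose. Escalation cohorts have 3 to 9 evaluable subjects (Protocol 9.2.1.1) and safety-expansion cohorts up to 6, so one subject admitted by one rule and excluded by the other can visibly change a cohort's summary.

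**Working it through.** All times are days after first dose.

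**Inputs**
- Duration clock: first SD or better, to first PD or death (Protocol 2.2.2; SAP 7.3.4).
- DCR membership: CR or PR, which need not be confirmed, or SD at 49 days or later, before first PD (SAP 7.3.4).
- First scheduled scan: 8 weeks, ±7 days (Protocol 7.7.1.1.2 and Table 12).
- Scans before day 49 are possible, either clinically indicated (Protocol 7.7.1.1.2) or at end of treatment (Table 12, footnote k).

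**Step 1. Reproduce the 49 days.** 8 × 7 − 7 = 49, as the SAP states. The late edge of the window is 8 × 7 + 7 = 63. The minimum is therefore the early edge of the Week 8 window, and SD at an on-schedule first scan always meets it.

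**Step 2. Apply both rules to example histories.** Duration = day of PD or death − day of first SD or better.

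| History | Counted in DCR? | Duration as defined |
|---|---|---|
| SD 49, PD 112 | Yes | 112 − 49 = 63, event |
| SD 56, PD 112 | Yes | 112 − 56 = 56, event |
| SD 63, PD 112 | Yes | 112 − 63 = 49, event |
| SD 35, PD 56 | No (PD) | 56 − 35 = 21, event |
| SD 35, no later assessment | No (NE) | Clock starts at 35; end depends on a censoring rule that is not stated |
| SD 35, SD 56, PD 112 | Yes | 112 − 35 = 77, event |

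Rows 1 to 3 agree on membership. Rows 4 and 5 do not: DCR excludes the subject and the duration analysis includes them. That is the defect.

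**Step 3. Restrict the duration to the DCR numerator.** Rows 4 and 5 drop out and the other rows are unchanged. Row 6 stays at 77 days, against 112 − 56 = 56 from the first scan that meets the 49-day rule. The 21-day difference comes from when the subject was scanned, and the restriction does not remove it.

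**Step 4. Check whether the 49-day rule produces zero durations.** Take a single SD scan at day 56.
- PD at day 112: 112 − 56 = 56, event.
- Death at day 90: 90 − 56 = 34, event.
- Neither, and no later valid scan: 56 − 56 = 0, censored, if the progression-free survival (PFS) rule in SAP Table 7 is borrowed.

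This subject already meets the 49-day rule, so that rule does not cause the zero. It arises because the clock would start and be censored at the same scan.

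**The case against.** The strongest reply is that the mismatch is rare. The 49 days was set at the window edge, scans follow fixed calendar dates, and an on-schedule first scan cannot produce the conflict. This stands and limits the point. It does not remove it, because the end-of-treatment scan is itself part of the schedule: a subject who stops for toxicity before day 49 may have SD on that scan and nothing after it.

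A second reply is that starting at first documentation is a consistent choice, stated the same way in Protocol and SAP and parallel to duration of response. This also stands. The start date is not the error; the missing link to the DCR set is.

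A third reply is that the endpoint is descriptive. Protocol 9.3 plans no formal tests, no decision rule uses this duration, and the swim plots and response listings show individual courses. This is fair and keeps the matter modest.

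Two stronger readings are tempting. A reader might infer that anyone with a single SD scan scores zero days. The documents do not support that: later PD or death gives a positive time, and SAP 7.3.3 extends Table 7 censoring only to duration of response. Even if it is borrowed, the result is an observation censored at time 0, not a measured zero. A reader might also infer that 49 days from first dose is the SAP's own duration clock, so that about 8 weeks are lost for every SD subject. The 49 days is a minimum for classifying SD; the SAP defines no disease-control duration from first dose.

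**Conclusion.** The point holds as an inconsistency within SAP 7.3.4. SD first reported before Day 49, then followed by PD or no further scan, is excluded from DCR but admitted to the duration of disease control in the same planned displays. Where PD is found at the Week 8 scan, the admitted value is a short event, 21 days in the example.

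The conclusion assumes only that the two definitions are applied as written and that at least one such early scan occurs. The effect cannot be sized: the documents do not say how many of the 52 subjects were scanned before day 49, or how many had SD on such a scan. A percentage from simulation would only return the assumed rate of early scans or dropout.

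The missing censoring rule for this endpoint is a separate gap. It governs the time-0 case and does not depend on the 49-day mismatch.

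**What to change.** In SAP 7.3.4, and in the endpoint definition in SAP 2.3.2, state that duration of disease control is computed only for subjects in the DCR numerator: CR, PR, or SD meeting the 49-day rule. The start date can stay as it is. The cost is one line of SAP text and no new data.

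One labelling note follows. DCR uses unconfirmed CR and PR, whereas Table 2.1.1.1 shows confirmed best response. Under SAP Table 4, an unconfirmed PR before day 49 followed by PD is still PD there. The table should say that its duration set is the DCR numerator.

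Moving the origin to first dose is optional and a matter of preference. It would largely repeat PFS in a subset selected for reaching a qualifying assessment. If wanted, it can be shown as a supplement labelled as measured from first dose, with the interval guaranteed by selection stated. While the section is open, the sponsor should also state a censoring rule for this duration, as a separate correction.

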HPV	human papillomavirus
ICF	informed consent form
ICH	International Conference on Harmonization
IDO	indoleamine 2,3-dioxygenase
IEC	independent ethics committee
IFN	interferon
IgG	immunoglobulin G
IL	interleukin
INR	international normalized ratio
Ipi	ipilimumab
irAE	immune-related adverse event
IRB	institutional review board
IRT	interactive response technology
IV	intravenous
mAb	monoclonal antibody
MedDRA	Medical Dictionary for Regulatory Activities
mRECIST	modified Response Evaluation Criteria in Solid Tumors
MRI	magnetic resonance imaging
MSI	microsatellite instability
MSI-H	microsatellite instability-high
MTD	maximum tolerated dose
NF-κB	nuclear factor kappa-light-chain-enhancer of activated B cells
Nivo	nivolumab
NK	natural killer
NSCLC	non-small cell lung cancer
ORR	objective response rate
OS	overall survival
OX40L	OX40 ligand
PAD	pharmacologically active dose
PD-1	programmed cell death protein 1
PD-L1	programmed cell death protein ligand 1
PFS	progression-free survival
PK	pharmacokinetic

Abbreviation	Definition
Pos	probability of success
PR	partial response
PT	prothrombin time
Q2W	every 2 weeks
Q6W	every 6 weeks
RCC	renal cell carcinoma
RECIST	Response Evaluation Criteria in Solid Tumors
RNA	ribonucleic acid
SAE	serious adverse event
SCCHN	squamous cell carcinoma of the head and neck
SCLC	small cell lung cancer
SD	stable disease
SmPC	summary of product characteristics
TCR	T-cell receptor
TEAE	treatment emergent adverse event
Teff	effector T cells
TNBC	triple-negative breast cancer
TNF	tumor necrosis factor
TNFR	tumor necrosis factor receptor
TNFSF	tumor necrosis factor super family
Treg	regulatory T cell
ULN	upper limit of normal

1. INTRODUCTION

This is an open-label, nonrandomized, Phase 1/2 study to determine the safety and tolerability, define the MTD or PAD, and assess the preliminary efficacy of INCAGN01949 in combination with immune therapies. Phase 1 will consist of 2 parts. Dose escalation (Part 1) will use a 3 + 3 + 3 design to determine the PAD and/or MTD of INCAGN01949 in combination with immune therapies in subjects with selected immunogenic advanced or metastatic solid tumors. The safety expansion (Part 2) will further explore tolerated doses of INCAGN01949 given as a run-in of 2 doses followed by concomitant therapies. Phase 2 will further evaluate the safety, tolerability, preliminary efficacy [REDACTED] of INCAGN01949 in combination with immune therapies. Subjects with advanced or metastatic gastric cancer, SCCHN, NSCLC, and RCC considered to be refractory to PD-1/L1 will be enrolled into Phase 2. A Simon 2-stage design will be used with a stopping rule to allow for early termination of a particular cohort at the end of Stage 1 if insufficient responses are observed.

1.1. Background

1.1.1. The Role of the Immune System in Cancer

The immune system is composed of diverse sets of cells designed to protect a host from pathogens while distinguishing from host and foreign antigens. This immune response is controlled by a series of checks and balances to allow for robust immune responses to pathogens while preventing either an excessive inflammatory event or an autoimmune response. Through immune surveillance, the immune system has been shown to recognize, attack, and destroy tumor cells (Wolchok and Saenger 2008). Detailed analysis of CD8+ T cells and the ratio of CD8+ Teffs/ FoxP3+ Tregs seem to correlate with improved prognosis and long-term survival in many solid tumors (Nosho et al 2010, Chang et al 2014, Preston et al 2013). Although the immune system has been shown to recognize and reject a tumor, many tumors evade immune surveillance or develop mechanisms of resistance.

Targeting the immune system is a proven and effective approach for cancer therapies. FDA-approved checkpoint inhibitors, such as ipilimumab, nivolumab, pembrolizumab, atezolizumab, and avelumab allow for the immune response to continue to proliferate in spite of inhibitory signals. The activation of costimulatory pathways through OX40 is another promising treatment approach and is the focus of this clinical study.

1.1.2. OX40 and the Tumor Necrosis Factor Super Family

OX40 (CD134) is a member of the TNFR superfamily. Other members of the TNFR superfamily include CD40, CD27, FAS, DR3, GITR, and 4-1BB. The TNFR superfamily has been shown to play a role in the regulation of the activation, proliferation, or apoptosis of lymphocytes (Weinberg et al 2000).

OX40 is a 227 amino acid protein that has a cytoplasmic tail, a transmembrane domain, and an extracellular region that contains 3 complete and 1 truncated cysteine-rich domains (Jensen et al 2010, Croft et al 2010). OX40L (also known as CD252) is thought to be the only ligand for OX40 and is thought to only bind to OX40 (Croft et al 2010).

Expression of OX40 has been observed on activated T cells (including CD4+ T cells, CD8+ T cells, and Tregs) (Weinberg et al 2011). OX40 expression is up-regulated on the surface of T cells after TCR engagement and costimulation through CD28 or the presence of inflammatory cytokines, including IL-1, IL-2, and TNF- α (Weinberg et al 2000, Jensen et al 2010). Following antigen activation of naive T cells, OX40 expression occurs between 24 hours and 4 to 5 days following TCR engagement. The upregulation of OX40 on memory T cells after the rechallenge of antigen occurs much more rapidly (within 4 hours) compared with naive T cells (Jensen et al 2010, Croft et al 2009, Gramaglia et al 1998).

Several groups have demonstrated that OX40 is expressed on T cells in the tumor microenvironment. In samples surgically obtained from patients with breast cancer, OX40 expressing T cells were observed in areas surrounding tumor cells, and those cells were thought to be tumor-specific T cells (Weinberg et al 2000). Other groups have shown that OX40+ T cells are present in samples from patients with melanoma, head and neck cancer, breast cancer, and colon cancer (Petty et al 2002, Ladányi et al 2004, Weinberg et al 2000, Vetto et al 1997). In addition, it is thought that the proportion of OX40+ T cells may correlate with improved survival (Petty et al 2002, Ladányi et al 2004).

OX40L is mainly expressed on antigen-presenting cells that include B cells, dendritic cells, endothelial cells, and macrophages (Weinberg et al 2000). OX40L is not expressed at high levels in noninflamed tissues, but is observed at sites of active autoimmune disease. To date, OX40L has not been identified within the tumor microenvironment (Gough et al 2008, Weinberg et al 2011).

Given its role in immune activation, targeting OX40 with an agonistic antibody would be expected to enhance the response of memory and Teff to tumor-specific antigens. The use of an antibody with ADCC capabilities may also selectively deplete Tregs (Gonzalez et al 2016, Bulliard et al 2013). Therefore the use of an anti-OX40 mAb with both agonistic and ADCC properties may be beneficial in boosting the immune response to malignant cells within the body. This hypothesis will be tested in this study.

1.1.3. *In Vitro* and *In Vivo* Evaluation of OX40

Several groups have explored the function of OX40 using both *in vitro* and *in vivo* models. OX40 signaling has been shown to promote T-cell division and survival, suppress the differentiation of Tregs, and modulate cytokine production and signaling. One way this is thought to occur is that OX40L binding to the OX40 receptor results in intracellular recruitment of TNFR-associated molecules, which then activates the NF- κ B pathway known to be important in cell survival (Jensen et al 2010). This is consistent with the observation that OX40 receptor engagement has been shown to increase survival, cytokine production, and migration of CD4+ T cells; increase granzyme B, IFN- γ , and perforin production of CD8+ T cells; and increase proliferation and overcome the anergic state in both CD4+ and CD8+ T cells (Moran et al 2013, Weinberg et al 2000).

Murine studies have shown that OX40 agonists promote tumor-specific memory T-cell expansion leading to rejection of tumor growth after inoculation with 4 different tumor cell lines ([Weinberg et al 2000](#)). Subsequent experiments performed in mice with established tumors showed that administration of an OX40 agonist led to an increase in the number of CD8+ T cells at the tumor site ([Gough et al 2008](#)). This combined with the lack of OX40L expression in the tumor environment indicates that there is a lack of OX40 signaling in the tumor microenvironment and provides additional rationale for OX40 agonist therapy in cancer.

While a contributing factor to the improved proportion of CD8+ T cells to Tregs is likely the activation and proliferation of CD8+ T cells after OX40 engagement, the role of Treg depletion must also be considered. Several studies have shown that OX40 expression is highest in the population of Treg cells within a tumor ([Bulliard et al 2014](#), [Marabelle et al 2013](#)). OX40 has been shown to inhibit the suppressing ability of Tregs ([Kroemer et al 2007](#), [Valzasina et al 2005](#)). OX40 has been shown to suppress Treg development and function *in vitro*, and in *in vivo* studies, the population of CD4+CD25+FoxP3+ Treg cells was decreased following treatment with an OX40 agonist ([Gough et al 2008](#)). Bulliard et al (2014) demonstrated that the administration of an agonistic anti-OX40 mAb induced the depletion of Tregs via an Fc γ R-mediated ADCC/ADCP manner. Experiments performed in mice showed that this mechanism contributed to the control of tumor growth in mice ([Bulliard et al 2014](#)).

